Undernutrition is a common problem in patients with cystic fibrosis (CF) despite international consensus that the patients shall be given 120-200% of energy recommendations. Studies imply that one problem might be that the patients are not compensated for the essential fatty acid deficiency (linoleic acid, LA), which is well known in these patients. This deficiency is shown not to be due to fat malabsorption, but associated to an increased turnover of arachidonic acid, a transformation product of LA. This abnormality is related to mutations associated with a more severe clinical phenotype. The most common and typical symptom of LA deficiency is poor growth. Studies in animals have further indicated that many of the symptoms in CF are related to the deficiency. A series of recent prospective studies from Wisconsin corroborate the importance of LA for growth. In Sweden LA has been supplemented to most patients since the late 70', and the condition of patients have been among the leading in the world regarding growth, pulmonary function and survival. Short-term studies have shown better effect of LA supplementation compared to similar supply of energy without including extra LA. There are few long-term studies, performed before the gene was identified, giving very heterogeneous patient groups in regard to genotype, but some positive results on growth and physiology. It's of interest that modern personalized extremely expensive therapy with correctors and potentiators for Cystic Fibrosis Transmembrane Conductance Regulator may influence lipid metabolism. LA might thus tentatively be a cheap adjuvant to this modern therapy, but this has to be specially studied.

The benefit for the patients would be great if the expected positive effect can be proved in the planned study. ***The treatment will be cheap and without adverse effects.*** From socioeconomic point of view is would be a great advantage.

AIM

To investigate the impact of long-term supplementation of fatty acids on clinical status and metabolism in patients with cystic fibrosis (CF).

DESIGN

A double-blind controlled randomized study of supplementation of linoleic acid (LA) compared to oleic acid (OA), and with long-chain omega 3 fatty acid (DHA) for one year to patients with CF.

BACKGROUND

CF is a systemic disease with major clinical symptoms from the gastrointestinal tract, predominantly pancreatic insufficiency and hepatobiliary disease, and from the lungs. Although survival has increased during the latest decades it is still a fatal disease with a high therapeutic burden and high percentage of impaired growth despite recommendations of very high energy intake, also in early infancy (Shoff et al 2006; Munck et al. 2018). Underweight is common both in children and adults with CF (NACFF Patient Register, ECFS Patient Registry).

It has been known for more than 50 years that patients with CF have low levels of the essential fatty acid linoleic acid (18:2w6, LA) and also that the long-chain polyunsaturated fatty acid (LCPUFA) docosahexaenoic acid (22:6w3, DHA) may be decreased in plasma and tissues (Kuo et al. 1962, Underwood et al. 1972, Freedman et al 2004). After 1975, when a newborn temporarily recovered in pancreatic

function after Intralipid® administration (Elliott et al.1975), some short-term trials with LA or high energy diets including LA have been performed showing a positive association to growth (van Egmont et al 1996, Steinkamp et al 2000) and pulmonary function (Chase et al 1979, Mischler et al 1986, Walkowiak J 2007, Maqbool et al 2008, Hjelte et al 2008, Lai et al. 2009). A few long-term studies have indicated beneficial effect of intravenous linoleic acid supplementation (Chase et al 1979, Kusoffsky 1983, Strandvik et al 1989, Strandvik et al 1994). In comparison, exclusive high energy intake does not have the same effect (van Egmont et al 1996, Steinkamp et al 2000, Aldámez-Echevarria et al 2013, Munck et al 2018). One study combining omega-6 and omega-3 fatty acids showed marked improvement in several parameters, compared to supplementation with only omega-3 fatty acids, which rarely gives any clinical benefit (Oliveira et al. 2010, Oliver et al. 2011, Alicandro G et al. 2013). In a small long-term controlled supplementation study performed before the gene was identified, improvement was seen in renal, liver and bile acid parameters (Strandvik et al.1989, Strandvik et al. 1994). Long-term treatment increased LA in many organs (Mischler et al 1986). Very long-term treatment with omega-6 rich oils and Intralipid® have resulted in exceptionally good clinical conditions regarding growth, bone mineral density, pulmonary function, reduction of pulmonary exacerbations and low clinical infectious status in a relatively large patient cohort, i.e. most of the Swedish patients with CF, compared with other international centers (Strandvik 1988; Strandvik 2006, Gronowitz et al.2004). The role of LA in these observations are supported by studies finding better growth and lung function in patients with higher LA concentrations in serum

(Maqbool et al 2008). However, there is a lack of long-term randomized controlled studies. Other treatment modalities, such as increased physical activity from early age, also introduced in the Swedish patients in the late 80's (Blomqvist et al. 1988), have probably also a large impact on the good clinical status of the Swedish patients.

It was shown more than 30 years ago that the LA deficiency was not due to malabsorption, but probably to an increased release of arachidonic acid (20:4w6, AA), causing an increased metabolism of LA, resulting in LA deficiency (Carlstedt-Duke et al. 1986, Strandvik et al 1988) and increase of eicosanoid metabolites (Strandvik Seybert 1996, Jabr et al 2013). Many studies in animals and cells have confirmed the hypothesis of high turnover (for review see Strandvik 2010). A hypothesis with an algorithm was formed to explain the mechanisms for the different symptoms (Strandvik 1989, Strandvik 1992) supported in later studies. From studies of newborns diagnosed by neonatal screening, it has been shown that 80% of patients with meconium ileus have markers of LA deficiency, high Mead acid and EFA index (T/T ratio), and similar markers were increased in around 50 % of patients without meconium ileus (Lai et al 2000). A relative improvement occurred during infancy, but again the markers deteriorate in late toddler age to prepuberty (Lai et al 2000), which coincides with the dip in growth in the patients as illustrated in both the European and North American CF patient registers. The Wisconsin CF Neonatal Screening Group have followed their patients in a series of papers and showed that intake of LA up to 2 years of age resulted in higher plasma LA concentrations with an OR of 7.46 for maintaining high LA if intake was > 5% of total

energy intake and both high energy and LA concentration increased the possibility to recover in weight to 2 years of age (OR 30.6, p=0.002). They conclude that “maintaining normal plasma LA for a prolonged period in addition to sustaining a high energy intake may be important in facilitating adequate weight gain” (Shoff et al 2006). These early “responders” also required lower energy intake to maintain adequate growth (Lai et al 2009), which is similar to our observation that patient who received regular LA supplementation had normal weight without increasing the energy intake (Kindstedt-Arfwidson et al 1988). In a follow up study the Wisconsin group found that the early response in growth was associated with better growth and lung function up to 12 years of age and in this paper they also included patients with meconium ileus, who initially had a more severe LA deficiency and they were also later much worse off (Sanders et al. 2018). They summarize that “Further studies are needed to identify optimal CF interventions that can maximize the chance for achieving early growth recovery” (Sanders et al 2018).

People with CF have low IGF-1 concentrations (Switzer et al 2009; Rogan et al 2010; Bessich et al 2013), and the low IGF-I concentrations correlates with lean body mass (Sermet-Gaudelus et al 2003), which usually is low in patients with CF, except in the LA supplied Swedish population (Gronowitz et al. 2008). In transgenic CF rats low IGF-1 levels correlated with impaired growth and bone content (Stalvey et al 2017). Studies have shown that low LA concentrations are associated with low IGF-1 levels in infants (Kjellberg et al 2018) and in animals (Korotkova et al 2004 and 2005). Other factors for poor growth might be an increased caloric demand, and it has been shown that severe CF phenotype is associated with an increased basic

metabolic turn-over (O'Rawe et al 1992). In rats with essential fatty acid deficiency an increased basal respiration has been reported (Rafael et al 1984). Furthermore, the increased intestinal permeability, which relates to membrane phospholipid layers, is correlated to the clinically more severe phenotypes in patients with CF (Hallberg et al 1997).

The cause of the low DHA is not clear, but the improvement of DHA by LA supplementation suggests that it might not be of primary importance (Farrell et al 1985, Strandvik et al 2001) and maybe associated with a high phospholipid turn-over (Bhura-Bandali et al. 2000, Strandvik 2010, Rogiers et al 1984). However, long-term studies in CF mice and a recent paper suggest that the ratio between AA/DHA in blood cell tissues is related to the liver disease in CF, suggesting that the concentrations of polyunsaturated fatty acids (PUFA) might contribute to the unexplained liver affection in many of the patients (Lindblad et al. 1999; Beharry et al. 2007; van Biervliet et al 2010; Jørgensen et al. 2012, Drzymala-Cryz et al, 2017). Because one study of transgenic CF mice showed low DHA associated with morphological changes in ileum and pancreas (Freedman et al 1999), although later not confirmed in a long-time study (Beharry et al 2007), many clinical trials with supplementation of omega-3 LCPUFA started, but mainly failed to show clinical improvement despite marked increase of omega-3 fatty acids in plasma (van Biervliet et al. 2008, Oliver et al. 2011, Alicandro et al. 2013). One study with regular intravenous supplementation of omega-3 for 3 months even showed negative impact on the patients (Durieu et al. 2007). As mentioned above one study showed

marked clinical improvement by a combination of omega-3 and omega-6 supplementation (Oliveira et al. 2010).

It is well known that low LA concentrations are associated with high AA concentration, while supplementation with LA decreases the AA concentration (Liou et al. 2007, Friesen et al 2010, Bjermo H et al 2012, Wheelock & Strandvik 2020). In healthy individuals no increase of inflammatory markers have been reported with omega-6 supplementation (Bjermo et al 2012, Johnson GH & Fritsche K 2012). This is of importance since the release of AA is the rate-limiting step for eicosanoid production, which is increased in CF (Strandvik a Seybert 1996, Chase & Dupont 1978, Jabr et al 2013). In one study of 10 months supplementation of LA in CF patients prostaglandin F2 α production decreased (Chase & Dupont 1978). Ivacaftror did not influence LA concentration but decreased AA concentration in plasma and decreased PGE-M in urine in the GOAL study for patients with G551D mutations (O'Connor & Siegmiller 2016). These studies show that both LA and CFTR modulators might influence lipid metabolism and decrease inflammatory mediators. Despite this fact, the lack of good randomized clinical studies have made many centers hesitate to supply LA because it's a substrate for AA and thereby also for the pro-inflammatory lipid mediators. High AA concentrations have been found in bronchial secretions in CF (Gilljam et al 1986) and was confirmed in a recent study of sputum from CF patients (Yang J, et al 2012)

In a recent double-blind randomized trial high AA concentration in plasma was associated with low NO in the airways of CF patients (Keen et al. 2010). Low NO can contribute to pseudomonas colonization, which is considered a threat for

progression of the pulmonary damage. Furthermore many studies have shown that OA increases compensatory when LA decreases (Christophe et al 1994), and it was shown in Toronto, (contributing to their persistent use of high fat diet when rest of the world prescribed low fat diet to CF) that high OA stimulated the growth of *Staphylococcus aureus*, the first colonizer of the airways in patients with CF (Campbell et al.1983). Similar imbalance of LA and OA was also found to impair the oxygen pressure influencing the hemoglobin oxygenation which would be a factor increasing the airway pathology in CF (Campbell et al 1976). Thus, it seems important to increase LA concentration and reduce AA concentration in the patients with CF also from reported pulmonary associations (Wheelock & Strandvik 2020). Many studies have shown that the pulmonary symptoms are the most affected persistent problem in the neonatally screened patients despite their high caloric diet, and improved early growth is associated with better pulmonary function up to 12 years of age (Sanders et al 2018).

It is also important that the hyperactivity of the epithelial sodium channel (ENaC), which is shown to contribute to the pulmonary symptoms, seem to be normalized by LA supplementation, as notified in sweat glands and kidneys (Strandvik 2021), and which might be an effect of the protein-lipid interaction. In recent studies the interaction of modulators and phospholipids have been shown (Liessi et al.2020; Kopp et al.2018 .

The recent discovery of the importance of the long-chain PUFA of the omega-3 series for the normal inflammatory response by transformation to prosolving specialized markers (SPM), the anti- inflammatory lipoxines (Rogeiero et al. 2012)

may indicate that supply of omega-3 fatty acids might be important as a general treatment for CF patients with their chronic airway inflammation. Further improvement might therefore be expected with a combined supplementation, especially since the long-chain omega-3 fatty acids inhibit delta-6 desaturase and thereby may further reduce the transformation of LA to AA (Hagve et al 1988).

WORKING PLAN

Patients and Eligibility.

Patients with CF, carrying 2 severe mutations referred to Class I and II, i.e. mutations associated with more severe LA deficiency and more severe clinical symptoms, (like delF508, 394delTT) are included after informed consent. The reason for including only those with clinically more severe phenotype is that those have pancreatic insufficiency and also other symptoms more expressively related to genotype (see above). Exclusion criteria will be pregnancy and transplantation and age above 15 and below 5 years (due to pulmonary function tests) and severe liver disease (cirrhosis, portal hypertension). The patients shall not have taken any lipid supplements for 2 months before inclusion and not be treated with any modulators (like Orkambi, Trikafta).

The patients will keep to their ordinary treatment of PERT and vitamins and that for the pulmonary symptoms and infections. No special dietary recommendations will be given, but PERT might be increased, when the supplement is given and that shall be registered. Number of pulmonary exacerbations and type of treatment, including antibiotics, are registered and also compared with the year before the study.

Sample size

A sample of 84 patients (42 per group) will ensure that a two-sided test with α =0.05 has 80% power to detect a 0.5 mean difference in 1-year change in weight-

for-age Z-score, assuming a pooled standard deviation of 0.8. This last figure has been obtained from a previous intervention study on cystic fibrosis patients (Alicandro et al. 2013). Since we expect a withdrawal rate of close to 10%, we planned to enroll 90 patients (45 per groups). The patients and caregivers will be informed by oral and written information and included after informed consent. The study is approved by local Ethic Committees and by the one at Karolinska Institutet and the study is performed according to the Helsinki Declaration.

Design

The study is designed as a double-blind randomized clinical trial

The patients will be randomized to either

- treatment A: linoleic acid (12 g for children 5-15 years) + 600 mg algeal DHA
- treatment B: oleic acid (12 g for children 5-15 years) + 600 mg algeal DHA

The fatty acids will be given daily for 12 months, in vials containing an emulsion of totally 20 ml (provided by AKK Company, Karlshamn, Sweden and Copenhagen Denmark, packed by WinterMedic, Odense, Denmark), which can be mixed with milk, juice, sour cream, porridge or any similar feeding at breakfast time. Some extra enzymes may be added.

The treatment will last 12 months, starting and ending at time of the yearly check up of the patients. Half the number of patients will be randomly allocated to receive either treatment A or B. An independent researcher (not involved in the study) will generate the allocation sequence at each center. This will reduce small differences in local treatment policy. The vials with supplementation will only be coded (black or white capsula) so neither patient nor caregivers or staff in charge will be informed by the type of supplementation.

Primary Outcome

- BMI Z-score, weight-Z-score

Secondary outcomes

- Height Z-score
- FEV1 (% of predicted) and oxygen saturation
- Exacerbations and infectious parameters compared to year before.
- Plasma phospholipid fatty acid profile.
- Plasma concentration of IGF-I

Explanatory outcomes

- Bone mineral density
- Lean body mass and fat mass.
- Liver function tests
- Lipid mediators (like eicosanoids and docosanoids)
- Cytokines
- 8-iso-prostane
- Sweat sodium and chloride concentrations
- Renal sodium excretion
- Resting energy expenditure
- Intestinal function (fecal calprotectin and fat absorption coefficient)
- Oral glucose tolerance with insulin determination.

METHODS

Patients will be screened for enrollment and will be allocated to one of the treatment at baseline visit. Follow-up visits will be scheduled at 6 and 12 months after treatment allocation. Some measures, like fat absorption coefficient and calprotectin and resting energy expenditure, exhaled NO and ergometer test will not be performed in all patients due to limited capacity at some centres. The study procedures are summarized in table 1.

Table 1. Outline of study procedures

	Baseline visit: Screening and allocation	+6 months	+12 months
Anthropometry	X	X	X
DXA	X		X
FFQ	X	X	X
24-h dietary recall	X	X	X
Pulmonary function	X		X
Blood sample	X	X	X
F-Calprotectin	X		X
Urine sample	X		X
Ergometer test with oxygen saturation	X		X
Oral glucose tolerance	X		X
Indirect calorimetry	X		X
Sweat test	X		X
Compliance to treatment	X	X	X
CF Questionnaire	X	X	X

1. *Anthropometry.*

Height and weight are controlled with the same equipment for each patient at respective centre and at each scheduled visit (baseline, 6 and 12 months after allocation). Z-scores of weight, height and BMI will be computed using WHO as growth standard. DXA is performed at start and after 12 months period for determination of bone mineral content and density, lean body mass and fat mass.

1. *Food registration.*

- Food frequency questionnaire (FFQ) will be performed at start and each scheduled visit, mainly used for calculation of energy intake and intake of fat and fatty acids (validated questionnaire Eriksson S et al. 2010). Since the products are different in different countries the FFQ form can only suggest **type** of products to be evaluated, complemented by the local dietician. The reason to include these registrations is to individually make a comparison with intake at start and end of study possible, checking that not major changes have occurred in diet, which can influence the results.
- 24-hour recall will be performed at start, 6 months and 12 months after allocation as a complement to FFQ for portion size, type of products etc.

3. *Pulmonary function.*

- Routine pulmonary function (FEV1) at each clinical visit
- Full spirometry at start and end of treatment
- Exhaled NO (if available)
- Ergometer test at start and end
- Oxygen saturation (ear-tip).

4. *Biochemistry.*

- Routine blood biochemistry (fasting) at start and end of treatment period, including Hb, platelets, white blood cell count and differential count, ASAT, ALAT, alkaline phosphatase, GGT, PK, total and conjugated bilirubin, bile acids, cholesterol, lipoproteins, triglycerides, urea, creatinine, glomerulus filtration rate. Ig-G, CRP, sedimentation rate.

- 1 ml serum/plasma for later analyses (to freezer divided in 4 tubes for later analyses of lipid mediators at KI).
- 0,5 ml for IGF-I analysis (to freezer for later analysis in Sweden)
- 0.5 ml plasma for cytokines (to freezer for sending to Stockholm for analyses (OLINK, Uppsala, Sweden).
- 0.5 ml plasma for analyses of phospholipid fatty acids (to freezer for later analysis in Poznan or Stockholm).
- Urine sample for routine tests, incl sodium and creatinine concentrations.

5. *Intestinal function*

- F-Calprotectin at start and after 12 months (in freezer for later analyses at one center)
- Fat absorption at start and 12 months. Three day dietary recording and feces

Sampling. Mixture in local laboratory with freezing of an aliquote for later transport to Poznan

6. *Metabolic tests*

- Urine sample for 8-isoprostanate and lipid mediators as eicosanoids, docosanoids and linoleic acid metabolites (directly to freezer -80 each sample in 2 x 8 ml and in 4 x 2 ml) for later analyses in Stockholm.
- Indirect calorimetry at start and after 12 months (if available in the hospital).
- Sweat test at start and after 12 months. **Both sodium** and chloride analyses.
- Oral glucose tolerance test.

7. *Quality of life.*

Quality of life will be assessed through the CF Questionnaire Revised (CFQ), a disease-specific tool that measures health-related quality of life in patients with

CF. There are different versions of the questionnaire: two for children over 6 years, one to be completed by the child and one to be completed by parent (CFQ Child and CFQ-Parent, respectively).

8. Compliance with the treatment

Compliance with the treatment will be evaluated by monthly contact with the study coordinator of respective centre, when not used vials will be registered and new supplied. The patients are asked to make a dairy over the daily intake also reported monthly to the coordinator. Extent of physical activity shall be notified.

9. Statistics

All data will be collected in identical Excel files and analysed in one center at end study.

The main analysis will be carried out on the intention-to-treat population defined as all randomized patients. We will also conduct a secondary analysis on the per-protocol population excluding patients not receiving the allocated treatment for more than 2 months.

Between-treatment differences in the primary outcome across time points will be evaluated by fitting random intercept linear mixed-effects models. Mixed effects model can account for intra-correlated repeated measures on the same subjects and accommodate missing data due to dropouts. The models will include the z-score of BMI as response variable, treatment, time and time x treatment interaction as independent variables. The model coefficients for the time x treatment interaction will be considered an estimate of the treatment effect on changes in the study outcome. Time will be included in the model as categorical variable with the following categories: baseline (pre-treatment), +6 months and +12 months from treatment allocation.

Secondary and explanatory outcomes will be compared across treatment groups using the paired t-test for normally distributed variables, otherwise the non-parametric Wilcoxon signed-rank test for dependent samples will be used.

A stratified analysis by sex will be performed.

RISK-BENEFIT

There will be no adverse effects to expect of this treatment , since the control group will have the same treatment as offered generally to patients, i.e. extra calories. The extra LA will not exceed the general intake in US (Choque et al 2014). Both groups get similar amount of omega-3 fatty acids; dose in agreement with general recommendations. The extra burden of investigations is small since the patients always have more extensive investigations at the yearly checkup.

IMPORTANCE

If clinical status is improved the patients in both groups will be asked for the possibility to continue with Group A therapy for one further year (requires new ethical applications). Furthermore, good result would indicate a multicenter study for treatment from diagnosis in countries with neonatal screening, which would be extremely important since many of the symptoms start early and especially the supply of high caloric diet gives many problems in patients and parents, and unsatisfying results, It can also have the potential to be a cheap complement to modern expensive drug treatment.

A special benefit for individuals and society would be if this simple, cheap and non hazardous treatment can reduce the enormous costs of the modern drug treatment, which is further not always available.

References:

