## 9. Statistics

All data will be collected in identical Excel files and analysed in one center at end study.

The main analysis will be carried out on the intention-to-treat population defined as all randomized patients. We will also conduct a secondary analysis on the per-protocol population excluding patients not receiving the allocated treatment for more than 2 months.

Between-treatment differences in the primary outcome across time points will be evaluated by fitting random intercept linear mixed-effects models. Mixed effects model can account for intra-correlated repeated measures on the same subjects and accommodate missing data due to dropouts. The models will include the z-score of BMI as response variable, treatment, time and time x treatment interaction as independent variables. The model coefficients for the time x treatment interaction will be considered an estimate of the treatment effect on changes in the study outcome. Time will be included in the model as categorical variable with the following categories: baseline (pre-treatment), +6 months and +12 months from treatment allocation.

Secondary and explanatory outcomes will be compared across treatment groups using the paired t-test for normally distributed variables, otherwise the non-parametric Wilcoxon signed-rank test for dependent samples will be used.

A stratified analysis by sex will be performed.

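### Enrolling 90 does not keep the required 84 patients at the expected withdrawal of close to 10%, though power stays at about 79–80%

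*Protocol*

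**What the plan says.** The Sample size section of the Protocol bases the trial on a between-group difference of 0.5 in the 1-year change in weight-for-age Z-score, with a pooled SD of 0.8 and 80% power: "A sample of 84 patients (42 per group) will ensure that a two-sided test with" α = 0.05 has that power. It then moves to the enrolment target: "Since we expect a withdrawal rate of close to 10%, we planned to enroll 90 patients (45 per groups". No inflation formula is given, and withdrawal is not defined.

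Three other statements bear on what a withdrawal costs:

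- SAP section 9 (same text in Protocol section 9): "The main analysis will be carried out on the intention-to-treat population defined as all randomized patients".
- Protocol section 9: "We will also conduct a secondary analysis on the per-protocol population excluding patients not receiving the allocated treatment for more than 2 months". Time off treatment therefore removes a patient only from the secondary analysis.
- Protocol, Design: "The treatment will last 12 months, starting and ending at time of the yearly check up of the patients". A patient who stops the supplement may still be weighed at the routine visit.

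The SAP contains no sample size or withdrawal figure.

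**The concern.** The sentence presents 90 as the consequence of the expected withdrawal rate. A reader will take it that 90 is 84 enlarged so that 84 remain after withdrawals, and will find that it is not: the increase from 84 to 90 covers a loss of 6.7%, which is hard to describe as close to 10%.

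What is at stake is the accuracy of a stated figure. If the gap were large, the trial could miss its 80% power target at a withdrawal rate the sponsor itself expects. The check therefore has two parts: whether the figures fit, and how much power is lost if they do not.

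**Working it through.** **Inputs (Protocol, Sample size).** Difference 0.5; SD 0.8; two-sided α 0.05; power 80%; 84 required (42 per group); withdrawal close to 10%; 90 enrolled (45 per group). Equal allocation is from the Design section.

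**Step 1. Reproduce the 84.** The standardised difference is 0.5/0.8 = 0.625.

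- Normal approximation: n per group = 2 × (1.960 + 0.842)² / 0.625² = 40.19, so 41 per group (82 in total).
- Two-sample t-test: n per group = 41.17, so 42 per group (84 in total), with power 80.8%.

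The stated 84 is right and matches the t-test.

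**Step 2. Try to reproduce the 90.**

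- Loss that 90 allows before falling below 84: 1 − 84/90 = 6.7%, or 6 patients.
- Division by the retained fraction: 84/0.90 = 93.3.
- Simple mark-up: 84 × 1.10 = 92.4.

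Neither formula gives 90. A looser reading of the rate does not help. Patients left from 90 are 83.7 at 7%, 82.8 at 8%, 81.9 at 9% and 81.0 at 10%.

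**Step 3. Power at the numbers retained.** This is a complete-case comparison of the 1-year change in weight-for-age Z-score.

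| Patients with 12-month data | t-test | Normal approximation |
|---|---|---|
| 45 + 45 (no loss) | 83.5% | 84.3% |
| 42 + 42 (84) | 80.8% | 81.7% |
| 42 + 41 (83) | 80.3% | 81.2% |
| 41 + 41 (82) | 79.8% | 80.8% |
| 41 + 40 (81, i.e. 10% loss) | 79.3% | 80.3% |
| 45 + 36 (81, all 9 losses in one group) | 78.8% | 79.8% |

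**Step 4. Allow for withdrawn patients who are still weighed.** With 9 withdrawals of whom k have a 12-month weight, 81 + k patients are available. Keeping 84 needs k of at least 3, which restores power to 80.8% (t-test) or 81.7% (normal). The plan does not say that this is expected.

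**Scope.** These figures concern weight-for-age Z-score, on which the sample size is based. The mixed model is specified for another variable ("The models will include the z-score of BMI as response variable") and plays no part in them.

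**The case against.** Four points can be made for the plan as written.

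1. *The Protocol never says that 84 must remain after withdrawals.* This is correct: the link is inferred from the sentence's wording. It is the natural reading, because 84 is the only requirement stated and withdrawal is the only reason given for exceeding it. The condition should still be kept in view.

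2. *What matters is 80% power, and 90 can deliver it at 10% loss.* By the normal approximation the unrounded requirement is 40.19 per group, and 40.19/0.9 = 44.7, so 45 per group is enough. By the t-test it is 41.17/0.9 = 45.7, so 45 falls just short. The Protocol's own 84 matches the t-test. This narrows the gap to a fraction of a patient per group but does not make 90 follow from 84.

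3. *The stated rate is approximate.* At 8% about 83 patients remain, with 80.3% power by t-test. Over 8–10% the shortfall against 84 is one to three patients. This stands as a statement of size; the rate that fits is still 6.7%.

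4. *Withdrawal need not remove a patient from the analysis.* All randomized patients are analysed, the mixed model is intended to cope with dropout, and Table 1 schedules anthropometry at 6 months as well, so a late withdrawal still contributes. This is fair, and the true loss of information may be smaller than the complete-case figures suggest. However, the sponsor enlarged the sample for withdrawal and so treated it as a loss, and the model is set out for BMI Z-score while the power calculation is for weight.

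These points limit the consequence. None of them makes the three figures consistent.

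**Conclusion.** The inconsistency is real and minor. The 84 is correct; the step from 84 to 90 does not correspond to withdrawal of close to 10%, and nothing else in the documents reconciles it. At 10% loss the trial would be 3 patients short of 84. Power would be 79.3% by t-test or 80.3% by normal approximation, a fall of about 1.5 points from its value at 84 and within 1 point of the 80% target. If all 9 losses fell in one group it would be 78.8% or 79.8%.

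This rests on two assumptions: that 90 was intended to keep 84, and, for the power figures, that no withdrawn patient has a 12-month weight. If at least 3 of 9 do, the shortfall disappears. The finding does not show an underpowered trial and gives no reason to recruit more patients.

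**What to change.** Keep 90 and restate the sentence in the Sample size section, for example:

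> We plan to enrol 90 patients (45 per group). This leaves 84 with 12-month data if no more than 6.7% withdraw. At the expected rate of close to 10%, and if no withdrawn patient is measured at 12 months, about 81 remain, giving about 79–80% power for the 1-year change in weight-for-age Z-score.

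A shorter version would also do: that 90 allows for about 7% loss, or that it gives about 80% power after 10% loss. The mixed model should stay out of this paragraph, because it is specified for BMI Z-score.

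The cost is one or two sentences, with no added patients, visits or analyses. The only concession is that power at the expected withdrawal rate reads as about 79–80% instead of 80%.
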